10.2.3 Response Criteria

PRIMARY (SOFT TISSUE) TUMOR RESPONSE¹

RESPONSE	ANATOMICAL IMAGING + MIBG (FDG-PET²) IMAGING
Complete Response (CR)	
• < 10 mm residual soft tissue at primary site, AND• complete resolution of MIBG or FDG-PET uptake (for MIBG non-avid tumors) at primary site
Partial Response (PR)	
• ≥ 30% decrease in longest diameter (LD) of primary site• MIBG or FDG-PET uptake at primary site stable, improved or resolved
Progressive Disease (PD)	
• > 20% increase in longest diameter taking as reference the smallest sum on study (this includes the baseline sum if that is the smallest on study), AND• a minimum absolute increase of 5 mm in longest dimension³
Stable Disease (SD)	Neither sufficient shrinkage for PR nor sufficient increase for PD at the primary site

¹Not for use in assessment of metastatic sites

² For ¹²³I-MIBG non-avid tumors

³ A mass that has not met PD measurement criteria but has fluctuating ¹²³I-MIBG avidity will not be considered progressive disease.

RESPONSE AT METASTATIC SOFT TISSUE AND BONE SITES⁵

RESPONSE	ANATOMICAL IMAGING + MIBG (FDG-PET ¹) IMAGING
Complete Response (CR)	
 Resolution of all sites of disease defined as: 
 Non-primary target and non-target lesions measure < 10 mm AND Lymph nodes identified as target lesions decrease to a short axis < 15 mm, AND MIBG uptake or FDG-PET uptake (for MIBG non-avid tumors) of non-primary lesions resolves completely
Partial Response (PR)	
 ≥ 30% decrease in sum of diameters² of non-primary target lesions compared to baseline, AND all of the following: 
 Non-target lesions may be stable or smaller in size AND No new lesions AND ≥ 50% reduction in MIBG absolute bone score (Relative MIBG bone score ≥ 0.1 to ≤ 0.5 using as a reference the absolute score for bone lesions from time of enrollment^{4,6}) or ≥ 50% reduction in number of FDG-PET avid bone lesions^{3,4}

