Progressive Disease (PD)	Any of the following: 
 Any new soft tissue lesion detected by CT or MRI that is also MIBG avid or FDG-PET avid; Any new soft tissue lesion seen on anatomic imaging that is biopsied and confirmed to be a neuroblastoma or ganglioneuroblastoma; Any new bone site that is MIBG avid and that was not seen on the immediate prior scan; A new bone site that is FDG-PET avid (for MIBG non-avid tumors) AND has CT or MRI findings consistent with tumor OR has been confirmed histologically to be neuroblastoma or ganglioneuroblastoma; > 20% increase in longest diameter taking as reference the smallest sum on study (this includes the baseline sum if that is the smallest on study), AND a minimum absolute increase of 5 mm in sum of diameters of target soft tissue lesions; Relative MIBG score ≥ 1.2 using as reference the lowest absolute score for bone lesions since enrollment^{4,7}
Stable Disease (SD)	Neither sufficient shrinkage for PR nor sufficient increase for PD of non-primary lesions

¹ Used for MIBG non-avid tumors² Sum of diameters is defined as the sum of the short axis of discrete lymph nodes (i.e., cervical, axillary nodes) added to the sum of the longest diameters of non-lymph node soft tissue metastases. Masses of conglomerate non-discrete lymph nodes will be measured using longest diameter.

³ For patients with soft tissue metastatic disease, resolution of MIBG and/or FDG-PET uptake at the soft tissue sites is not required; all size reduction criteria must be fulfilled.

⁴ MIBG-SPECT or MIBG-SPECT/CT may be used for scoring purposes but the same imaging methodology should be used for all evaluations.

⁵ Criteria for soft tissue metastasis not applicable if the patient has only bone metastasis; criteria for bone metastasis not applicable if the patient has only soft tissue metastasis.

⁶ Relative Curie score when assessing patient for partial response: [Current Curie score for bone sites] / [Curie score for bone sites at enrollment].

⁷ Relative Curie score when assessing patient for progressive disease: [Current Curie score for bone sites] / [Lowest Curie score for bone sites since enrollment].

BONE MARROW RESPONSE

RESPONSE	BONE MARROW STATUS ¹
Complete response (CR)	Bone marrow with no tumor infiltration upon reassessment, independent of baseline tumor involvement

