Progressive disease (PD)	Any of the following: 
 • Bone marrow without tumor infiltration that becomes > 5% tumor infiltration upon reassessment; or • Bone marrow with tumor infiltration that increases by > 2-fold and has > 20% tumor infiltration upon reassessment.
Minimal disease (MD)	Any of the following: 
 • Bone marrow with \leq 5% tumor infiltration and remains > 0-\leq 5% tumor infiltration upon reassessment; or • Bone marrow with no tumor infiltration that becomes \leq 5% tumor infiltration upon reassessment; or • Bone marrow with >5% tumor infiltration that has > 0-\leq 5% tumor infiltration upon reassessment.
Stable disease (SD)	Bone marrow with tumor infiltration that remains positive with > 5% tumor infiltration upon reassessment but does not meet CR, MD or PD criteria

¹Immunohistochemistry strongly encouraged

DETERMINATION OF OVERALL RESPONSE

In determining overall response, Not Fully Evaluated (NFE) will be used when at least one component of response evaluation was not required and not performed for one or more of the 3 components required for overall response (this will be annotated CR, PR, MR, or SD).

If a component was not performed and was required by protocol, that component will be determined to be Not Done (ND) and the overall response will be Not Done.

RESPONSE	CRITERIA
Complete Response (CR)	All components meet criteria for CR
Partial Response (PR)	PR in at least one component and all other components are either CR, MD (Bone marrow), PR (Soft tissue or Bone) or Not involved (NI); no component with PD.
Minor Response (MR)	PR or CR in at least one component but at least one other component with SD; no component with PD.*
Stable Disease (SD)	SD in one component with no better than SD or NI in any other component; no component with PD.
Progressive Disease (PD)	Any component with PD

NI = Not involved, site not involved at study entry and remains not involved; MD = Minimal Disease, for bone marrow assessment only.

For CR, PR, MR, SD – if one or more component evaluations were not required at that disease evaluation timepoint *AND* they were not performed at the timepoint in question—that response will be annotated as Not Fully Evaluated (NFE).

*Patients who enroll with marrow-only disease who have a marrow response of Minimal Disease will also be coded as having an overall response of Stable Disease.

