APPENDIX IX: CURIE SCORING SUMMARY SHEET (Submit this sheet via RAVE)

COG Registration Number: _____ Radiology reviewer: _____
(6 digits) (print name)

Date of scan: _____ Type of Scan (check 1): I-123 MIBG I-131 MIBG
(DD/MM/YYYY)

Scan time point (circle 1): Baseline End of Cycle 2
End of Cycle 4 End of Cycle 6 End of Cycle 10
End of Cycle 14 End of Cycle 17 Relapse/Progression Other (specify)
Note: For patients enrolled with Amendment 4 or later, the End of Cycle 6 timepoint will be the end of therapy. Please do not fill out End of Cycles 10, 14, and 17 as those timepoints are not relevant.

[figure not shown]
Table 1a. Scoring skeletal disease

Regions 1 – 9	
Scoring	MIBG uptake
0	No MIBG uptake
1	1 focal site
2	> 1 focal site
3	≥ 50% of a region

Table 1b. Scoring soft tissue disease

Region 10 (Primary soft tissue site)	
Scoring	MIBG uptake
0	No soft tissue uptake
1	1 focal soft tissue site
2	> 1 focal soft tissue site
3	≥ 50% of a region (chest, abdomen)

Region	Site	Curie score
1	Head / Neck	
2	Cervico-Thoracic spine	
3	Ribs / Sternum / Clavicles/ Chest	
4	Lumbar / Sacral spine	
5	Abdomen/Pelvis	
6	Upper Extremity (Proximal)	
7	Upper Extremity (Distal)	
8	Lower Extremity (Proximal)	
9	Lower Extremity (Distal)	

10	Soft Tissue	
TOTAL	Total scores from Regions 1 - 10	

Figure 1.

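### The bone partial-response rule contradicts itself below a relative MIBG score of 0.1, leaving some of the deepest bone responses to be coded as either PR or SD

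*Combined protocol and SAP*

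**What the plan says.** The table in Section 10.2.3 for metastatic soft tissue and bone sites gives these rules for MIBG-avid disease:

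- **CR:** "MIBG uptake or FDG-PET uptake (for MIBG non-avid tumors) of non-primary lesions resolves completely", together with size limits for soft tissue lesions and nodes.
- **PR:** a 30% or greater fall in the sum of diameters, no new lesions, and "≥ 50% reduction in MIBG absolute bone score (Relative MIBG bone score ≥ 0.1 to ≤ 0.5", measured against enrollment.
- **SD:** "Neither sufficient shrinkage for PR nor sufficient increase for PD of non-primary lesions".

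Footnote 6 computes the relative score for PR as "Current Curie score for bone sites] / [Curie score for bone sites at enrollment". Footnote 5 adds: "Criteria for soft tissue metastasis not applicable if the patient has only bone metastasis". For a patient with bone metastases only, the bone criterion therefore decides this component alone.

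Components then combine. Overall MR is "PR or CR in at least one component but at least one other component with SD; no component with PD". Overall SD is "SD in one component with no better than SD or NI in any other component; no component with PD". Section 9.3.1 counts as responders those whose best overall response by the end of Cycle 6, on central review, is MR or better. Every eligible patient stays in the denominator. Section 9.3.3 bases the interim comparison on response after Cycle 2.

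**The concern.** The PR line states one condition in two ways that do not agree. A fall of at least half is met by every relative score from 0.5 down to 0. The bracket accepts only 0.1 to 0.5. Scores below 0.1 that are not CR meet the first statement and fail the second, and if the second governs, SD is the only category left.

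The floor has no counterpart nearby. The FDG-PET half of the same bullet asks for a 50% or greater fall in avid bone lesions with no lower limit, and PR at the primary site has none either. Under the bracket, the same depth of bone clearance could be PR on PET and SD on MIBG.

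At stake is the primary endpoint. The ambiguity touches patients whose bone disease has nearly or wholly cleared, and some of them could be counted as non-responders.

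**Working it through.** **1. The plan's own figure.** No design figure is in dispute, but the sample size in Section 9.3.1.1 rests on this endpoint. Inputs: 40% versus 60%, one-sided alpha 0.20, power 80%, continuity-corrected test with pooled variance. Both z-values are 0.8416 and d = 0.20.

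- Uncorrected: n₀ = [0.8416·√(2·0.5·0.5) + 0.8416·√(0.24 + 0.24)]² / 0.04 = 34.7, so 35.
- Corrected: n = (n₀/4)·[1 + √(1 + 4/(n₀·d))]² = 44.1, so 45 per arm. The plan's figure reproduces.
- Power at 45 per arm: Φ[(0.20 − 1/45 − 0.8416·√(0.5/45)) / √(0.48/45)] = Φ(0.862) = 80.6%.

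**2. The rows side by side.**

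| Situation | CR? | PR by the words? | PR by the bracket? |
|---|---|---|---|
| Score 0, all other CR conditions met | yes | – | – |
| Relative score above 0 and below 0.1 | no | yes | **no** |
| Relative score 0.1 to 0.5 | no | yes | yes |
| Score 0, soft tissue metastases at least 30% smaller but short of CR | no | yes | **no** |

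Rows 2 and 4 are the conflict. Row 4 arises because 0 divided by any baseline is 0, which is also below 0.1. Section 10.2.2.6 and the table footnotes do not settle it. Appendix XIV only combines component labels already assigned.

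**3. Can row 2 occur?** Appendix IX ("Table 1a. Scoring skeletal disease") scores regions 1–9 from 0 to 3, so the bone maximum is 9 × 3 = 27. Requiring 0 < residual/baseline < 0.1 in whole numbers:

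- Residual 1 needs a baseline of at least 11 (1/11 = 0.091; 1/10 = 0.10 is inside the bracket): baselines 11–27, 17 pairs.
- Residual 2 needs a baseline of at least 21 (2/21 = 0.095; 2/20 = 0.10): baselines 21–27, 7 pairs.
- Residual 3 never qualifies (3/27 = 0.111).

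That is 17 + 7 = 24 pairs, out of 182 with residual uptake and a relative score of at most 0.5. These are score combinations, not patients. Section 10.2.2.6 describes the relative score without limiting it to bone. On the full scale (maximum 30) the count is 20 + 10 = 30, and the conclusion is the same.

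**4. Effect on overall response (Appendix XIV; order primary / soft tissue and bone / marrow).**

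| Other components | Coded SD | Coded PR |
|---|---|---|
| NI / · / NI | SD | PR |
| NI / · / MD | SD | PR |
| SD / · / NI | SD | MR |
| SD / · / MD | SD | MR |
| NI / · / CR | MR | PR |

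In the first four rows the coding decides responder status. Marrow improvement to minimal disease does not offset it. PR or CR in another component does, as in the last row.

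**5. Size.** One patient in an arm of 45 is 1/45 = 2.2 percentage points. At the interim look on the first 40 eligible patients (about 20 per arm under 1:1 allocation), one patient is about 1/20 = 5 points. The futility trigger there is simply a lower observed rate on Regimen B, and no earlier on-treatment evaluation exists to offset a Cycle 2 reading.

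The documents give no frequency, so the following is an assumed range: the share of true responders coded as non-responders, and the resulting power.

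| Share lost | Both arms | Regimen B only |
|---|---|---|
| 1% | 80.0% | 78.9% |
| 2.5% | 79.2% | 76.3% |
| 5% | 77.8% | 71.5% |
| 10% | 75.0% | 61.0% |

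The rule is the same in both arms, and nothing in the documents points to a loss confined to Regimen B.

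**The case against.** A reader might infer that anyone with more than 90% but incomplete clearance is simply neither CR nor PR, and so a non-responder. The documents do not support that. The leading words of the PR line have no floor, and clearance above 90% is hard to call insufficient shrinkage, which is what the SD row requires. A central reviewer may reasonably assign PR, and nothing shows that the floor is being applied.

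The endpoint is also forgiving. It takes the best response over the evaluations after Cycles 2, 4 and 6. A patient who passes through 0.1–0.5 on the way down, or who clears fully later, is already a responder provided no component shows PD.

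The size is not an estimate of bias. Any single misclassification is 2.2 points, and the true number could be zero. Finally, the protocol adopts published response criteria, and the documents do not show whether the bracket comes from them.

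All of this stands, and it limits the reach of the point. It does not remove the contradiction: two careful readers can code the same scan differently, and the text does not say who is right. If the bracket was inherited, the protocol's own wording still conflicts with itself.

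**Conclusion.** The point holds as an unresolved contradiction in a rule that feeds the primary endpoint, not as a demonstrated misclassification. A patient is lost only if all three conditions hold: the reader follows the bracket; no other component has PR or CR at that evaluation; and no other evaluation through Cycle 6 gives MR or better. Incomplete clearance above 90% also requires a baseline bone score of at least 11. Bone score 0 with residual metastatic soft tissue can arise from any positive baseline bone score.

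The expected number affected cannot be computed without a baseline Curie distribution. The power figures are illustrations under assumed rates, and the planned 45 per arm does not change. The Cycle 2 interim comparison is the more exposed use, because best response over later evaluations cannot help there. The matter should be settled before the primary analysis.

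**What to change.** In the PR row of Section 10.2.3, replace the bracket with: relative MIBG bone score ≤ 0.5, not meeting CR. This covers both groups. The more obvious repair, a range above 0 and up to 0.5, would still exclude a bone score of 0 with residual metastatic soft tissue. State that the change clarifies how the adopted response criteria are applied.

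Apply it identically to both regimens. Recheck the recorded central-review scores, including the Cycle 2 reads, blind to regimen, and document the result before the primary analysis.

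The cost is one phrase, a scan of recorded scores for relative values below 0.1, and a noted clarification of the cited criteria. The sample size and the test stay as they are.

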10.2.4 Duration of Response

10.2.4.1 Duration of overall response: The duration of overall response is measured from the time measurement criteria are met for CR, PR, or MR (whichever is first recorded, even if annotated as NFE) until the first date that recurrent or progressive disease is objectively documented (taking as reference for progressive disease the smallest measurements recorded since the treatment started).

The duration of overall CR is measured from the time measurement criteria are first met for CR until the first date that progressive disease is objectively documented.

10.2.4.2 Duration of stable disease: Stable disease is measured from the start of the treatment until the criteria for progression are met, taking as reference the smallest measurements recorded since the treatment started, including the baseline measurements.

10.2.5 Progression-Free Survival (PFS)

For PFS, time to event will be calculated from the time of randomization to first occurrence of relapse, progressive disease, or death. Patients without a PFS event will be censored at the time of last follow-up.

10.2.6 Response Review

All patients will have central review of imaging after Cycles 2, 4, and 6 to evaluate for response. See [Section 15.2](#) for central review imaging guidelines and submission requirements.

11.0 ADVERSE EVENT REPORTING REQUIREMENTS

11.1 Purpose

Adverse event (AE) data collection and reporting, which are required as part of every clinical trial, are done to ensure the safety of patients enrolled in the studies as well as those who will enroll in future studies using similar agents. Certain adverse events must be reported in an expedited manner to allow for timelier monitoring of patient safety and care. The following sections provide information about expedited reporting.

11.2 Determination of reporting requirements

Reporting requirements may include the following considerations: 1) whether the patient has received an investigational or commercial agent; 2) the characteristics of the adverse event including the *grade* (severity), the *relationship to the study therapy* (attribution), and the *prior experience* (expectedness) of the adverse event; 3) the Phase (1, 2, or 3) of the trial; and 4) whether or not hospitalization or prolongation of hospitalization was associated with the event.

An investigational agent is a protocol drug administered under an Investigational New Drug Application (IND). In some instances, the investigational agent may be available commercially, but is actually being tested for indications not included in the approved package label.

Commercial agents are those agents not provided under an IND but obtained instead from a commercial source. The NCI, rather than a commercial distributor, may on some occasions distribute commercial agents for a trial.

When a study includes both investigational and commercial agents, the following rules apply.

- *Concurrent administration:* When an investigational agent is used in combination with a commercial agent, the combination is considered to be investigational and expedited reporting of adverse events would follow the guidelines for investigational agents.
- *Sequential administration:* When a study includes an investigational agent and a commercial agent on the same study arm, but the commercial agent is given for a period of time prior to starting the investigational agent, expedited reporting of adverse events that occur prior to starting the investigational agent would follow the guidelines for commercial agents. Once therapy with the investigational agent is initiated, all expedited reporting of adverse events follow the investigational agent reporting guidelines.

11.3 Expedited Reporting Requirements – Serious Adverse Events (SAEs)

To ensure compliance with these regulations/this guidance, NCI requires that AEs be submitted according to the timeframes in the AE reporting tables assigned to the protocol, using the CTEP Adverse Event Reporting System (CTEP-AERS).

Any AE that is serious qualifies for expedited reporting. An AE is defined as any untoward medical occurrence associated with the use of a drug in humans, whether or not considered drug related. A Serious Adverse Event (SAE) is any adverse drug event (experience) occurring at any dose that results in ANY of the following outcomes:

- 1) Death.
- 2) A life-threatening adverse drug experience.
- 3) An adverse event resulting in inpatient hospitalization or prolongation of existing hospitalization (for \geq 24 hours). This does not include hospitalizations that are part of routine medical practice.
- 4) A persistent or significant incapacity or substantial disruption of the ability to conduct normal life functions.
- 5) A congenital anomaly/birth defect.
- 6) Important Medical Events (IME) that may not result in death, be life threatening, or require hospitalization may be considered a serious adverse drug experience when, based upon medical judgment, they may jeopardize the patient or subject and may require medical or surgical intervention to prevent one of the outcomes listed in this definition.

11.4 Special Situations for Expedited Reporting

11.4.1 SAEs Occurring More than 30 Days After Last Dose of Study Drug

Any Serious Adverse Event that occurs more than 30 days after the last administration of the investigational agent/intervention **and** has an attribution of a possible, probable, or definite relationship to the study therapy must be reported according to the CTEP-AERS reporting tables in this protocol.

11.4.2 Persistent or Significant Disabilities/Incapacities

Any AE that results in persistent or significant incapacity or substantial disruption of the ability to conduct normal life functions (formerly referred to as disabilities), congenital anomalies or birth defects, must be reported via CTEP-AERS if it occurs at any time following treatment with an agent under an NCI, COG, or industry sponsor IND/IDE since these are considered to be serious AEs.

11.4.3 Death

Reportable Categories of Death

- Death attributable to a CTCAE term.
- Death Neonatal: A disorder characterized by cessation of life during the first 28 days of life.
- Sudden Death NOS: A sudden (defined as instant or within one hour of the onset of symptoms) or an unobserved cessation of life that cannot be attributed to a CTCAE term associated with Grade 5.

- Death NOS: A cessation of life that cannot be attributed to a CTCAE term associated with Grade 5.
- Death due to progressive disease should be reported as Grade 5 “*Disease progression*” in the system organ class (SOC) “*General disorders and administration site conditions*.” Evidence that the death was a manifestation of underlying disease (e.g., radiological changes suggesting tumor growth or progression: clinical deterioration associated with a disease process) should be submitted.

Any death occurring ***within 30 days*** of the last dose, regardless of attribution to the investigational agent/intervention requires expedited reporting within 24 hours.

Any death occurring ***greater than 30 days*** after the last dose of the investigational agent/intervention requires expedited reporting within 24 hours **only if** it is possibly, probably, or definitely related to the investigational agent/intervention.

11.4.4 Secondary Malignancy

A ***secondary malignancy*** is a cancer caused by treatment for a previous malignancy (e.g., treatment with investigational agent/intervention, radiation or chemotherapy). A metastasis of the initial neoplasm is not considered a secondary malignancy.

All secondary malignancies that occur following treatment need to be reported via CTEP-AERS. Three options are available to describe the event:

- Leukemia secondary to oncology chemotherapy
- Myelodysplastic syndrome
- Treatment related secondary malignancy

Any malignancy possibly related to cancer treatment (including AML/MDS) must also be reported via the routine reporting mechanisms outlined in this protocol.

